#### 5.1. Imaging preparation

- 5.1.1. **Oral hydration.** Participants will be encouraged to maximize hydration the day before and day of  $^{68}\text{Ga}$  PSMA-HBED-CC imaging.
- 5.1.2. **Furosemide.** 20 mg furosemide (IV push) will be administered concurrently or immediately after radiotracer administration to minimize PET scatter artifacts from excreted radiotracer accumulation in the kidney and urinary

bladder.

- 5.1.3. **Contrast.** Imaging contrast will not be ordered as part of this study.
- 5.1.4. **Voiding.** Participants will be asked to void their bladder immediately prior to radiotracer injection and before imaging.

5.2. **Ga PSMA-HBED-CC administration**

- 5.2.1. **Dose.** 3-7 mCi (111 – 259 MBq). Target 5 mCi.
- 5.2.2. **Route of administration.** Intravenous.
- 5.2.3. **Frequency.** Once per PET scan.
- 5.2.4. **Uptake time.** 75 minutes ± 25 minutes. Target 75 minutes

5.3. **Prohibited Medications**

None.

5.4. **PET/CT Imaging Procedures**

- 5.4.1. **Scan coverage.** Scan coverage will extend from mid-thigh to the base of the skull, starting from the mid-thighs to prevent urinary bladder radiotracer accumulation at the start of PET imaging. Subject to void immediately prior to imaging.
- 5.4.2. **Bed position.** Scan time will be dependent on scanner capabilities. At a minimum, 3 minutes per bed position will be used.
- 5.4.3. **Discharge.** Subject must be monitored for adverse events for a minimum of 2 hours post-injection.
- 5.4.4. **Local Analysis.** A board-certified nuclear medicine physician on-site will interpret the images within 3 business days of the imaging study. These interpretations will not be used for final evaluation, however regional positivity results will be collected as study data.
- 5.4.5. **Internal Blinded Reads.** Imaging data will be interpreted by two different readers in a random order at separate reading sessions. Cross sectional imaging from the PET will be available for anatomic correlation. Final reads for each subject will be interpreted as positive or negative for the presence of pelvic nodal disease, and positive or negative for the presence of osseous metastatic disease and soft tissue metastases outside of the pelvis. All readers will have undergone Ga PSMA PET training.
- 5.4.6. **Results dissemination.** Results will be shared with the subject's urologist and will be included in the subject's medical record.

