## 6.4. **Follow-up**

6.4.1. **Pathology.** Results from pathology ordered per standard of care up to 12 months post Ga PSMA-HBED-CC PET/CT, will be obtained for study analysis.

6.4.2. **Follow-up imaging.** Conventional imaging ordered per standard of care up to 12 months post Ga PSMA-HBED-CC PET/CT, will be obtained for study analysis. If the 1st Ga-68 PSMA-HBED-CC PET/CT scan shows lesions outside the pelvic region AND if imaging is NOT obtained per standard of care the research study will obtain a CT (abdomen and pelvis w/ contrast if contrast not contraindicated). Readers will be unblinded to all results and will be specifically informed of the location of the Ga PSMA-HBED-CC PET positive lesions so follow-up measurements may be performed on the same lesions.

6.4.3. **Laboratory.** Results from laboratory reports related to prostate cancer monitoring (e.g. PSA levels) ordered per standard of care up to 12 months post Ga PSMA-HBED-CC PET/CT, will be obtained for study analysis.

6.4.4. **Second Ga PSMA-HBED-CC PET/CT (if medically indicated).** If the 1st Ga PSMA-HBED-CC PET/CT scan shows lymph nodes or visceral (soft tissue) lesions positive for prostate cancer disease, but surgery or biopsy results in negative pathology; the subject may be asked to return to complete a 2nd Ga-68 PSMA-HBED-CC PET/CT imaging visit.

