## 12.1. **$^{68}\text{Ga}$ -PSMA-HBED-CC PET Results Definition**

Imaging interpretation  $^{68}\text{Ga}$ -PSMA-HBED-CC PET:

**Local Interpretations:** PET images will initially be interpreted by a board certified nuclear medicine physician or a board-certified radiologist experienced in reading PET at the time of the imaging study at the institution that the study is being performed. These interpretations will not be used for evaluation of the primary endpoint.

**Blinded Read Logistics:** Imaging data will be de-identified. PET data will be interpreted by two different readers in a random order at separate reading sessions. Cross sectional imaging (CT or MRI) from the  $^{68}\text{Ga}$ -PSMA-HBED-CC PET will be available for anatomic correlate. The blinded readers will be blinded to all other imaging results and all other clinical data.

**Reader Positivity and Negativity Definition:** Sub-regions defined in Table 12.2 will be graded for the presence of suspected disease on a two-point scale by each reader (0=Negative or 1=Positive). A region will be judged as positive if at least one lesion in this region is visually positive..

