12.1.1.3. Bone lesions will be considered positive if the  $^{68}\text{Ga}$ -PSMA-

HBED-CC uptake is focal and greater than physiologic bone marrow.

- Bone lesions will be classified by further by region: spine, ribs, pelvis, extremities, skull, sternum, and clavicle, as Defined in Table 12.2. These sub-regions will be correlated with reference standard results in these sub-regions, however this sub-region data will not be directly used for evaluation of the primary or secondary endpoints, but for exploratory analysis.

12.1.1.4. Prostate bed and prostate lesions will be considered positive if the Ga-PSMA-HBED-CC uptake is focal and greater than physiologic background activity of the involvement organ or anatomic site.

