  - If PSA increases by more than 25% (PCWG3 definition of recurrence) on systemic therapy, then an increase in the size of lesion by more than 20% in the long axis diameter will be considered positive for disease.
- b. In subjects with localized suspected lesions(s) receiving targeted treatment without concomitant systemic treatment there are two ways to meet positive disease criteria:
  - If the subject demonstrates a decrease of PSA by greater than 50% after targeted treatment [OR]
  - If on post-treatment follow-up imaging within 3-12 months, lesions seen on CT or MRI decrease by more than 30% in long axis diameter (with a minimum of 3 mm in change in size)
- c. For untreated subjects: If on follow-up imaging within 3-12 months, lesions seen on CT or MRI increase by more than 20%

in long axis diameter (with a minimum of 3 mm in change in size).

ii. Negative for disease:

- Conventional Imaging follow up will not be used for assessment of negativity for disease

iii. Indeterminate for disease

- Regions with no visceral lesions determined to be positive by the conventional imaging criteria described above and without pathology will be designated as visceral regions indeterminate for prostate cancer disease.
- Prostate bed and prostate regions not determined to be positive by the conventional imaging criteria described above and without pathology will be designated as prostate regions indeterminate for prostate cancer disease.
- Subjects that have had neither pathology sampling, nor conventional imaging follow up will have all prostate and visceral regions designated as indeterminate for disease by reference standard.

12.2.2.3. Bone lesions will be considered:

i. Positive for disease on baseline assessment:

- Any positive sclerotic lesion on the CT portion of the Ga-PSMA-HBED-CC PET or on a separate CT obtained  $\leq$  30 days before or after the PET/CT.
- Focal uptake on the baseline bone scan performed within one month of Ga-PSMA-HBED-CC PET.
- Any MRI lesion in bone read as positive on the initial MRI performed within one month of Ga-PSMA-HBED-CC PET.

ii. Positive for disease on follow up:

- Any new positive sclerotic lesion on CT within 12 months of Ga-PSMA-HBED-CC PET scan
- Any new MRI bone lesion within 12 months of Ga-PSMA-HBED-CC PET scan
- Any new focal uptake in bone within 12 months of Ga-PSMA-HBED-CC PET scan

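### The CT from the index PSMA PET/CT can by itself confirm a bone lesion in the reference standard, which can raise the osseous PPV; report osseous results with and without regions confirmed only that way

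*Combined protocol and SAP*

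**What the plan says.** Section 12.2.2.3.i lists what makes a bone lesion reference-positive at baseline. The first item is "Any positive sclerotic lesion on the CT portion of the" index scan; the sentence continues "PET or on a separate CT obtained" within 30 days of it. The two sources are alternatives, so the index CT is sufficient. A bone scan or MRI within one month is also accepted.

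The PET call for bone rests on tracer uptake: positive if "uptake is focal and greater than physiologic bone marrow" (12.1.1.3). The blinded readers have the CT beside the PET. Section 5.4.5 states "Cross sectional imaging from the PET will be available for anatomic correlation", and section 12.1 says the cross-sectional imaging "will be available for anatomic correlate". Section 12.1 adds "The blinded readers will be blinded to all other imaging results and all other clinical data", which leaves the index CT in view.

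Section 13.3.1.3 counts a PET-positive osseous region as a true positive if it is positive by imaging under 12.2.2.3. Under 12.2.1 and 12.2.2 pathology ranks first, and imaging is used where pathology is not available. Under 12.2.2.3.iii and iv imaging cannot make bone negative; a region without positive imaging or pathology is indeterminate. Objective 1.2.1 names biopsy and imaging follow-up as the comparator for osseous metastases.

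**The concern.** A reference standard should be independent of the test it judges. Here one acquisition serves both sides: the reader can use the CT when making the PET call, and the same CT can then confirm that call. A benign sclerotic focus with some uptake is scored as a true positive although nothing outside the index session has been examined.

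The plan does not name who reads the index CT for the reference standard, or require that reading to be blind to the PET. For follow-up imaging, section 6.4.2 says "Readers will be unblinded to all results and will be specifically informed of the location of the" PET-positive lesions. Nor does the plan define what makes a sclerotic lesion positive.

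Bone is also the exception within the plan. Lymph nodes and visceral lesions need a change over time, in size or PSA (12.2.2.1, 12.2.2.2); only bone has a same-session rule.

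At stake are the osseous accuracy figures, one of three sub-classes in 13.3, and the summary over all imaged regions. The pilot's product is its estimates, and 13.1 intends to use them, possibly combined with other sites' results, to plan a larger study.

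**Working it through.** **The plan's own figure.** The only planning figures are the 95% half-widths for sensitivity at N = 30 (13.1). They reproduce: 1.96 × √(p(1−p)/30) gives 16.40, 15.49, 14.31, 12.78 and 10.74% for p = 70, 75, 80, 85 and 90%. None concerns bone, and this point does not depend on them.

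**The route to a true positive.**
1. The reader marks a bone region positive on uptake, with the index CT in view (5.4.5, 12.1, 12.1.1.3).
2. No pathology decides the region, so imaging does (12.2.2).
3. Sclerosis on the index CT makes it reference-positive (12.2.2.3.i).
4. It is a true positive (13.3.1.3).

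No other section requires a separate CT or an independent reading.

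**Effect on PPV (assumed inputs).** Let p be the true osseous PPV and b the share of false-positive PET bone regions with benign sclerosis on the index CT. Assume the other false-positive regions are scored false positive under 13.3.3.3 and every true metastasis is confirmed by some route. Then

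apparent PPV = p + (1 − p) × b

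| True PPV p | b = 10% | b = 25% | b = 50% |
|---|---|---|---|
| 50% | 55% | 62.5% | 75% |
| 70% | 73% | 77.5% | 85% |
| 90% | 91% | 92.5% | 95% |

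The gain is (1 − p) × b: from 0.10 × 0.10 = 1 point to 0.50 × 0.50 = 25 points over this grid.

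**Effect on sensitivity (assumed inputs).** Take 10% of bone regions diseased, true sensitivity 80% and specificity 95%. As shares of all regions: TP = 0.10 × 0.80 = 0.080, FN = 0.020, FP = 0.90 × 0.05 = 0.045, TN = 0.855. True PPV = 0.080/0.125 = 64%. Let b0 be the share of PET-negative disease-free regions with benign sclerosis on the index CT. Those move from TN to FN, since a region positive by imaging cannot be a true negative under 13.3.2.3.

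For b = 25%, b0 = 0:
- TP = 0.080 + 0.045 × 0.25 = 0.09125; FP = 0.03375
- sensitivity = 0.09125/0.11125 = 82.0%; PPV = 0.09125/0.125 = 73.0%

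For b = 25%, b0 = 5%:
- FN = 0.020 + 0.855 × 0.05 = 0.06275
- sensitivity = 0.09125/0.154 = 59.3%; PPV unchanged at 73.0%

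| b | b0 | Sensitivity | Specificity | PPV |
|---|---|---|---|---|
| 0 | 0 | 80.0% | 95.0% | 64.0% |
| 25% | 0 | 82.0% | 96.2% | 73.0% |
| 50% | 0 | 83.7% | 97.4% | 82.0% |
| 25% | 5% | 59.3% | 96.0% | 73.0% |
| 50% | 5% | 62.0% | 97.3% | 82.0% |

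PPV rises whenever b is above zero. Sensitivity rises slightly if benign sclerosis occurs only where the PET is positive, and falls if it also occurs in even a small share of PET-negative regions.

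**The case against.** The incorporation is only partial. The PET call rests on uptake and the reference on CT sclerosis, so the two can disagree. A PET-negative sclerotic lesion is scored as a false negative under 13.3.4.3 (as printed, that item speaks of a scan negative for extra-pelvic nodes, but its reference part concerns bone). This stands. A reader might infer that the rule must inflate sensitivity; the documents do not support that.

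A reader might also infer that a second PSMA PET could verify the first, because 12.2.2.3.ii accepts "Any new focal uptake in bone within 12 months of" the PSMA scan without naming a modality. That reading is weak. The second scan in 6.4.4 is triggered by nodes or soft-tissue lesions, not bone. Section 5.7.2 does not list PSMA PET among the follow-up for positive bone lesions. The criterion sits under conventional imaging in 12.2.2. Uptake must also be new, so persistence of the original focus does not qualify. What remains is a wording gap.

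Nor is it right that nothing counterbalances the rule. Section 13.3.3.3 provides for false-positive osseous regions, and under 12.2.1.3 pathology showing another PSMA-avid condition makes bone negative. The offset is incomplete, because 12.2.2.3.iii and iv leave a region without positive imaging or pathology indeterminate.

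Deleting the criterion would carry a cost. Sclerosis present at baseline is not new on a later CT, so some true metastases could lose their only confirmation. Section 13.1 also foresees combining results with sites using the same reference definitions. Both are good reasons to keep the definition and add an analysis.

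**Conclusion.** The point holds in limited form. Where no pathology decides, the CT of the index scan can alone confirm a bone lesion that the reader called with that CT in view. This can raise the apparent osseous PPV; its effect on sensitivity can go either way. It also departs from the comparator in objective 1.2.1. The baseline bone scan and MRI are not follow-up either, but they are at least separate from the index scan.

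The size cannot be determined from the documents. Every bone accuracy figure in the calculation is an assumption. The PPV gains also assume that unverified false-positive regions are scored false positive.

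A reader might infer a dramatic effect from small counts. Suppose six PET-positive bone regions, two of them benign with sclerosis on the index CT. The rule gives 6/6 = 100%. Without it, PPV is 4/6 = 67% only if both benign regions are scored false positive and the other four are still confirmed. If both become indeterminate and so non-evaluable (12.2.2.3.iv, 13.3.5), PPV is 4/4 = 100%, unchanged. The counts are invented and the plan does not settle the scoring, so neither result is a finding about this trial.

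The primary pelvic nodal endpoint is untouched, and the secondary results are descriptive with no significance testing. This is a cheap improvement to how a secondary result is reported.

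**What to change.** - Keep the definition in 12.2.2.3.i, for comparability with other sites.
- Record the verification source for each bone region: pathology, index CT, separate CT, bone scan, MRI, follow-up imaging or PSA response.
- In 13.3, pre-specify osseous and all-regions sensitivity, specificity, PPV and NPV with and without regions verified only by the index CT. Apply this to PET-positive and PET-negative regions alike.
- State how many of those regions become indeterminate or false positive, or, if PET-negative, true negative, once the index CT no longer counts. Without these counts the two sets of figures cannot be interpreted.
- As a minor clarification, name the modality for new focal uptake in 12.2.2.3.ii as non-PSMA imaging.

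The cost is one data field and one table, with no new scans or visits. The stricter analysis will have fewer evaluable bone regions. It may understate PPV if true metastases lose their only confirmation, so the two analyses should be read as a sensitivity comparison and not as guaranteed bounds.

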12.2.1.3. Bone lesions: Given the high rate of false negative biopsies for osseous metastases in subjects with prostate cancer, subjects with negative bone biopsies of  $^{68}\text{Ga}$ -PSMA-HBED-CC PET positive lesions will be further evaluated:

- If pathology demonstrates an alternative diagnoses that is known to be  $^{68}\text{Ga}$ -PSMA-HBED-CC positive (eg Renal Cell Carcinoma metastases, Paget's disease), then this will be considered negative for disease.
- If pathology is indeterminate, then follow-up imaging as described below will be performed as per clinical standards at the site.

12.2.1.4. Although not routinely performed during standard practice, immunohistochemical staining for PSMA of tumor specimens (primary and lymph node metastases) may be performed, although not required.

12.2.1.5. All regions not sampled for biopsy/histopathology will be designated as indeterminate for disease by pathology. Conventional imaging follow-up may be used in these cases to determine tissue status.

12.2.2. Follow-up Imaging will be used as a secondary assessment for prostate cancer in the event pathology information is not available:

All subjects will be tracked for follow-up conventional imaging between 3-12 months post  $^{68}\text{Ga}$ -PSMA-HBED-CC (dedicated CT, MRI and/or bone scan) as per site standard of care. If no follow-up imaging has been performed within the 9 months following the  $^{68}\text{Ga}$ -PSMA-HBED-CC scan, then the research study will pay for an additional follow-up CT scan to be performed in the 9-12

month window post-Ga-PSMA-HBED-CC scan. Follow up imaging will only be performed on subjects that have positive Ga-PSMA-HBED-CC findings because conventional imaging assessment for disease is primarily targeting suspicious lesions identified by Ga-PSMA-HBED-CC PET/CT. Interpretation of follow-up imaging will be performed by local read. Preferably, the follow-up conventional imaging should be the same modality/modalities as the initial staging work-up to allow for reproducible and accurate comparisons. Conventional imaging standards as described below will be used to determine tissue positive for prostate cancer disease. Conventional imaging will not be used to determine negative prostate cancer disease regions due to its inherently low negative predictive value.

Tissue positive for prostate cancer disease based on follow-up imaging:

12.2.2.1. Lymph nodes will be assessed by change in size.

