13.3.1. True positive region

13.3.1.1.  **$^{68}\text{Ga}$  PSMA-HBED-CC PET/CT positive for extra-pelvic node metastases by internal blind reader** – and pathology (if available) positive for that node, or, extra-pelvic node positive for disease by imaging as defined in Section 12.2.2.1.

13.3.1.2.  **$^{68}\text{Ga}$  PSMA-HBED-CC PET/CT positive for visceral metastases by internal blind reader** – and pathology (if available) positive for that visceral lesion, or, visceral lesion positive for disease by imaging as defined in Section 12.2.2.2.

13.3.1.3.  **$^{68}\text{Ga}$  PSMA-HBED-CC PET/CT positive for osseous metastases by internal blind reader** - and pathology (if available) positive for that osseous lesion, or, osseous lesion

positive for disease by imaging as defined in Section 12.2.2.3.

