13.3.4.2.  **$^{68}\text{Ga}$  PSMA-HBED-CC PET negative for extra-pelvic nodes by internal blind reader**, and pathology (if available) positive for that visceral lesion, or, visceral lesion positive for disease by imaging as defined in Section 12.2.2.2.

13.3.4.3.  **$^{68}\text{Ga}$  PSMA-HBED-CC PET negative for extra-pelvic nodes by internal blind reader**, and pathology (if available) positive for that osseous lesion, or, osseous lesion positive for disease by imaging as defined in Section 12.2.2.3.

13.3.5. Non-evaluable region:

13.3.5.1. Any region that does not have sufficient data to meet the criteria for definition of true positive region, true negative region, false positive region, or false negative region will be classified as non-evaluable.

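### Three bone-imaging lines in 12.2.2.3 count a finding as disease without a read as positive for metastasis, so benign findings that lack pathology can distort osseous sensitivity and PPV

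*Combined protocol and SAP*

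**What the plan says.** Section 12.2.2.3 lists the imaging findings that make bone reference-positive.

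- Baseline bone scan: "Focal uptake on the baseline bone scan performed within one month of" the PSMA PET.
- Follow-up uptake: "Any new focal uptake in bone within 12 months of" the PSMA PET. The follow-up MRI line likewise asks only that a bone lesion be new.
- Baseline MRI, by contrast: "Any MRI lesion in bone read as positive on the initial MRI performed within one month of" the PSMA PET.
- Baseline CT, by contrast: "Any positive sclerotic lesion on the CT portion of the" PET/CT. The follow-up CT line carries the same qualifier.

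Section 12.2.2.3 iii adds that conventional imaging is not used to establish negativity. Section 12.2.1.3 has a benign exception for bone, but it opens "If pathology demonstrates an alternative diagnoses that is known to be" PSMA-positive, so it needs a tissue result.

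Section 13.3 feeds these rules straight into the secondary endpoint. A PET-positive bone region is a true positive under 13.3.1.3 with "and pathology (if available) positive for that osseous lesion, or, osseous lesion" positive by imaging under 12.2.2.3. The false-negative rule 13.3.4.3 accepts an "osseous lesion positive for disease by imaging as defined in Section 12.2.2.3". Its PET condition, however, is a negative read for extra-pelvic nodes, not for bone.

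**The concern.** A bone scan can show focal uptake and still be reported as benign, for example from degenerative change or a healing fracture, neither of which the plan mentions. Under the bone-scan line the report does not matter: uptake alone makes the region reference-positive. Without pathology nothing in the plan reverses that, because imaging can only yield positive or indeterminate.

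Osseous sensitivity, specificity, PPV and NPV are secondary endpoints (1.2.1, 13.3). Benign findings counted as disease push sensitivity down when PET is negative and PPV up when PET is positive. With few true bone metastases among prostatectomy candidates, which is my assumption, one misclassified man is visible in the result. Section 13.1 also foresees combining results with sites that use the same reference definitions, which calls for a rule that two sites would apply alike.

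**Working it through.** **The plan's own figure.** The only calculation is the half-width table in 13.1, for n = 30. The formula 1.96 × √(p(1−p)/30) gives 16.4, 15.5, 14.3, 12.8 and 10.7% at p = 70, 75, 80, 85 and 90%. All five entries agree. The table is not specific to bone and is not in dispute.

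**The lines of 12.2.2.3 side by side.**

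| Line | Positivity condition |
|---|---|
| CT, baseline | positive lesion |
| Bone scan, baseline | none |
| MRI, baseline | read as positive |
| CT, follow-up | new and positive |
| MRI, follow-up | new only |
| Focal uptake, follow-up | new only |

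**How a benign finding travels.**

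- PET-negative man, benign uptake on a baseline scan within a month, no biopsy: reference-positive under 12.2.2.3 i. Without the uptake he could be a true negative under 13.3.2.3. With it he is a false negative, reading 13.3.4.3 as meant for bone.
- PET-positive benign lesion, benign uptake, no biopsy: a true positive under 13.3.1.3.
- Follow-up: 12.2.2 says follow-up imaging is performed only in men with positive PET findings. New findings there mostly turn false positives into hits. Misses could come only from standard-of-care imaging in PET-negative men, or from PET-positive men whose bone read was negative.

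**Lesion match.** In 13.3.1.3 the pathology arm refers back to the PET lesion; the imaging arm does not. The different-region rule for bone, 13.3.3.3.1, covers pathology only.

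**13.3.4.3 taken literally.** A man whose PET is positive for bone and negative for extra-pelvic nodes, with imaging-positive bone, satisfies both 13.3.1.3 and 13.3.4.3. This looks like a copying error.

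**Illustration 1 (assumed counts).** Suppose 2 true cases, both detected, and k PET-negative men with benign baseline uptake. Sensitivity = 2/(2 + k): 100% at k = 0, 2/3 = 67% at k = 1, 2/4 = 50% at k = 2.

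**Illustration 2 (assumed rates).** Let π be the share with true bone metastases, Se and Sp the PET bone accuracy, and b the share of metastasis-free men who had a scan and showed benign uptake, independent of PET. Each man contributes one bone region.

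- Apparent sensitivity = [πSe + (1−π)b(1−Sp)] / [π + (1−π)b].
- Take π = 10%, Se = 0.85, Sp = 0.95, b = 10%. Sensitivity = (0.085 + 0.0045)/(0.10 + 0.09) = 0.0895/0.19 = 0.47, against 0.85 at b = 0.
- PPV = 0.0895/(0.0895 + 0.0405) = 0.69, against 0.085/(0.085 + 0.045) = 0.65.
- Sensitivity is 0.60 at b = 5% and 0.34 at b = 20%.
- Follow-up in PET-positive men only, with 20% of PET false positives showing unrelated new uptake: PPV = (0.085 + 0.009)/0.13 = 0.72; sensitivity = 0.094/(0.094 + 0.015) = 0.86. Both move upward.

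The documents give none of these rates.

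**The case against.** The strongest defence is that a local reader would never call an arthritic joint a metastasis, and that the plan relies on such judgement. That is plausible in practice. But the neighbouring lines write the judgement in and these three do not, so the text invites different applications.

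Several limits stand:

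- Pathology takes precedence (12.2.1), and known Paget's disease is excluded (3.2.4), so only undiagnosed cases could enter by that route.
- A baseline bone scan is collected only if one was done (6.1.2), and the rule counts it only within one month.
- The endpoint is descriptive, in a 30-patient pilot, and the primary nodal endpoint is untouched.

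Some stronger readings are tempting but unsupported:

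- A reader might infer that the plan has no lesion matching for imaging. Section 13.3.3.3 concerns the PET-positive lesion itself, 12.2.2 says imaging mainly targets PET-identified lesions, and 6.4.2 tells follow-up readers where those are. Matching is intended; 13.3.1.3 merely fails to require it.
- A reader might infer that uptake on the optional second PSMA PET could serve as new focal uptake. Section 12.2.2 defines follow-up as conventional imaging (CT, MRI or bone scan), and 6.4.4 is triggered by nodal or soft-tissue lesions, not bone.
- A reader might picture arthritic uptake in a knee confirming a PET lesion. PET coverage runs from mid-thigh to skull base (5.4.1), and 13.3 reports on imaged regions.
- A reader might take the illustrations as forecasts. They rest on assumed counts and rates, and the number of scanned men is unknown and may be small.

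**Conclusion.** The point holds as a defect in a stated rule. Three lines of 12.2.2.3 let a finding reported as benign count as bone metastasis where no pathology settles it. Baseline uptake can err in either direction; follow-up findings mostly inflate the hits. The missing lesion link in 13.3.1.3 is a gap in wording against a clear intent.

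The size cannot be fixed from the documents. It is confined to a secondary endpoint, to men who had a bone scan or follow-up imaging, and to lesions without pathology. The 67% and 50% figures assume two true cases, both detected, and one or two benign baseline uptakes in PET-negative men. They show how fragile a small denominator is, not what to expect. Because the two biases oppose each other, they could not be removed afterwards without knowing the mix.

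**What to change.** 1. In 12.2.2.3, add to the baseline bone-scan line and to the follow-up uptake and MRI lines: *read as positive for metastasis; uptake or lesions attributed to a benign cause do not count*.
2. In 13.3.1.3, make the imaging arm refer to the same PET-positive osseous lesion, as the pathology arm does. State that PET-positive bone with only unmatched imaging findings is not a true positive, and is classified under 13.3.3.3 or as non-evaluable.
3. If matching is to use the bone sub-regions of Table 12-2, amend 12.1.1.3, which now reserves them for exploratory analysis. Otherwise the change creates a new contradiction.
4. In 13.3.4.3, replace the extra-pelvic-node condition with a negative PET read for osseous lesions.

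The cost is wording. Bone-scan reports are already collected (6.1.2) and follow-up imaging is already read locally (12.2.2). There are two downsides. Some equivocal lesions will become indeterminate and leave the osseous table. Follow-up readers know the PET locations (6.4.2), so their read is not independent of PET; the report should say so and give the number of osseous classifications that rest on it alone.
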